#### 6. Analysis Populations (Datasets)

According to the principles of intent to treat (ITT) analysis as defined in ICH E9, all participants who have been randomized will be considered as part of the ITT population... Participants will be tabulated based on treatment group to which they are randomized.

The Safety Population will include all participants who received at least one dose of study medication. Participants will be tabulated based on treatment group they actually received.

A Per Protocol (PP) population will be defined as all participants who received all 9 infusions. Participants will be tabulated based on treatment group they actually received.

#### 7. Statistical Methods

#### 7.1. General Statistical Consideration

All analysis (generation of Tables, Figures and Listings) will be performed using SAS 9.4 or newer.

All statistical Tables will summarize data by the following columns (or rows when summary Table is by treatment groups in rows) Low Dose, High Dose, Low & High Dose, Placebo, Total. If there are space limitations the Total column can be excluded. A footnote will clarify what Low and High Dose refer to.

All data collected on the eCRF will be included in the Listings. Some data will only be in Listings and no summary Tables or Figures will be created.

The eCRF collected participant initials and date of birth (The concatenation of these is variable SUBNUM in the dataset). For participant privacy this data will not be included in any Tables or Listings but will be retained in the analysis database. The Site ID and internal ID will be used to create a new unique Participant ID. In Listings this new Participant ID will be used as the unique identification of participants in this study.

Descriptive statistics for continuous data will include the mean, standard deviation, median, minimum, maximum, Q1, Q3.

Categorical data will be summarized by the frequency and percentages within each category. Unless otherwise specified the denominator for the %'s will be the number of participants randomized to the treatment group within the population summarized. Wherever applicable missing data will be summarized as a category.

F-SA-06-01, Version 5.0/30 Dec 2021, SOPs Link: SOP-SA-06

Sponsor: Cellavita Pesquisa Científica Ltda.

Protocol: ADORE-DH

All summary statistics will be displayed to 1 decimal place unless the data recorded is only at the decimal level in which case summary statistics will display data at one additional decimal place. Summary statistics such as minimum or maximum will be displayed as an integer or to the accuracy of data collected if it is only at the decimal level.

The p-value will be displayed up to 4 decimal places. If the p-value is less than 0.0001, it will be presented as' <.0001'; if the p-value is greater than 0.9999, it will be presented as '>.9999'.

Baseline will be defined as the last non-missing measurement before a participant received first treatment of study drug (At baseline visit of V0).

All descriptive statistical summaries and statistical inferences will be performed based on nominal visits (visits at which data are collected).

Early termination visits will be allocated to the nearest scheduled visit where data was to be collected but is not recorded.

All analyses of changes, % changes, etc. will be by scheduled visits.

For analyses of abnormalities, data from both scheduled visits and unscheduled visits will be included.

#### 7.2. Data Handling

#### 7.2.1. Premature Withdrawal and Missing Data

The following imputation rules will be used for prior and concomitant medications.

Partial or missing start date for concomitant medication

- 1. Incomplete or partial start date will not be imputed if end date of concomitant medication is on or before treatment start date.
- 2. Incomplete or missing start date will be imputed as mentioned below if end date of concomitant medication falls after treatment start date (or if medication is ongoing at EoS for treated participants).

Handling of partial/missing dates for Medication

Partial/Missing Start Date

- 1. Missing day Impute the 1st of the month unless month and year is same as month and year of first dose of study drug then impute first dose date.
- 2. Missing day and month impute 1st January unless year is the same as first dose date then impute first dose date.

Partial/Missing End Date

- 1. Missing day Impute the last day of the month unless month and year is same as month and year of last dose of study drug then impute last dose date.
- 2. Missing day and month impute 31st December unless year is the same as last dose date then impute last dose date.

No other imputation of missing data for safety assessments will be made. Wherever possible missing data will be summarized as a category.

No imputation for missing data will be made as the mixed model repeated measures incorporates missing data.

Additional analyses may be conducted for FDA, EMA or other regulatory agencies if required and deemed appropriate under assumptions of MAR and MNAR using MI.

The eCRF did not allow entry of partial AE dates so no imputation of start or stop dates will be performed.

#### 7.2.2. Derivation and Transformation on Data

Besides the calculation for some endpoints, which are based on data collected via eCRF, no derivation or transformation will be performed.

Age is auto calculated on the eCRF and the value will be used unless deemed inaccurate in which case Age will be computed as follows:

Age= (IC Signature Date-Date of Birth +1) /365.24, rounding to one decimal place

Duration of exposure will be defined as follows:

Exposure duration=Last dosing date - first dosing date +1

The CAP score refers to the term "-Age Product (CAP)", which is an index calculated in relation to the age and length of the CAG repetition.

The CAP score formula is: CAP= 100 x Age x (CAG -L)/S

CAG is the number of repetitions on chromosome 4 (considering the allele with the highest number of these repetitions) (Section 2.6.7). L and S are constants (L=30 and S=627). "L" anchors the CAG length at the lower end of the distribution relevant to the pathology of HD. "S" is a normalization constant chosen so that the CAP score is approximately 100 at the participant's expected age of onset, as estimated by Langbehn et al. 2004. For the calculation in this study, the value of S will be 627, which is an estimate obtained by a reanalysis of data from Langbehn et al presented by Warner and Hayden 2012.

An additional derived variable of pre-treatment rate of change (slope) per year will be computed and summarized for select efficacy parameters such as TMS, TFC, etc.

For TMS this is computed as follows:

Pre-Treatment TMS rate of change (slope) per year = (Baseline TMS Score - 0 which is the best TMS score) / Duration since onset of symptoms in years.

Similarly for TFC the pre-treatment rate of change (slope) per year is as follows:

Pre-Treatment TFC rate of change (slope) per year = (Baseline TFC Score - 13 which is the best TFC score) / Duration since onset of symptoms in years.

Based on review of above pre-treatment slope additional analyses may be performed to see effect of pre-treatment slope on post-treatment slope by analyzing the post-treatment minus the pre-treatment slope.

#### 7.3. Participants in Study

#### 7.3.1. Subject Disposition and Analysis Populations (Datasets)

Subject disposition will be summarized by tabulating the number and % of subjects screened, randomized and treated in each of the above-mentioned analysis populations (if they are different).

The table will also summarize the number and % of subjects who completed the study through Visit 11, the number of participants who discontinued along with reasons for discontinuation.

An additional Table will summarize the number and % of participants completing each visit.

#### 7.3.2. Protocol Deviation

Protocol deviations will only be included in the listings and no summary Table will be generated.

#### 7.3.3. Demographics and Baseline Characteristics

Demographics and baseline characteristics will summarize Age, Sex, Race, Dominant Hand, Education Level, Height, Weight, BMI, IMC Classification, CAP Score, Pre-Treatment TMS Slope, Pre-Treatment TFC Slope, Baseline primary and secondary efficacy assessments as described in Section 4.1.1 and 4.1.2.

#### 7.3.4. Medical History and Concomitant Medication

Medical History, Prior and Concomitant Medications will be summarized.

F-SA-06-01, Version 5.0/30 Dec 2021, SOPs Link: SOP-SA-06

#### 7.4. Efficacy Analysis

Efficacy analysis will be based on the primary and secondary efficacy endpoints as described in Sections 4.1.1 and 4.1.2.

#### 7.4.1. Analysis on Primary Efficacy Endpoint

The primary efficacy variable for this study is the rate of change (slope) per year from Baseline to Visit 11 in TMS.

The null hypothesis represents no difference between the two active treatment groups pooled together as compared to the placebo group:

H0:  $\mu_A = \mu_P$ HA:  $\mu_A \neq \mu_P$ 

Where  $\mu_A$  is the mean rate of change (slope) per year from Baseline to Visit 11 in TMS for participants randomized to either of the two active doses and  $\mu_P$  is the mean rate of change (slope) per year from Baseline to Visit 11in TMS for participants randomized to the placebo group.

Analysis will be performed on observed data using MMRM. The model will include the following effects: Treatment, Baseline TMS, Treatment \* Day interaction. Due to the small sample size of the study and the study visits not conducted as per schedule of assessments due to COVID-19, the model may be changed or alternative models analyzed.

The unstructured covariance matrix for repeated observations within participants will be used. If the model does not converge, then a simpler covariance structure with less parameters will be used, according to the following order:

- 1. Toeplitz with heterogeneity (TOEPH)
- 2. ARH(1),
- 3. CSH,
- 4. Toeplitz (TOEP)
- 5. AR(1), and
- 6. CS.

The least square mean and standard error of the least square mean for each treatment group, and the 95% CI for the comparisons will be presented at each post-baseline visit.

In addition, actual observed values and rate of change (slope)s per year from Baseline to V3, V7 and V11 will be summarized using descriptive statistics for continuous data.

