#### 4. Endpoints

#### 4.1. Efficacy Endpoints

#### 4.1.1. Primary Efficacy Endpoint

The primary efficacy endpoint is rate of change (slope) per year from Baseline to V11 in total motor score (TMS) from the UHDRS.

Baseline is defined as the last non-missing value prior to first infusion at V0. If a value was not collected at V0 the nearest prior non-missing value is used as the Baseline value.

The TMS Score is the sum of the 31 items in the Motor Assessment portion of UHDRS with each item rated 0 to 4. The TMS is between 0 (Best) to 124 (Worst).

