#### 4.1.2. Secondary Efficacy Endpoints

Secondary efficacy endpoints will include the following:

From UHDRS: TMS (at V7), Total Chorea Score (TCS), Total Functional Capacity (TFC), Functional Assessment (FA), Behavioral Assessment (BA), Independence Scale (IS), Cognitive assessments (CA) of (F, A and S combined, Digits Direct, Reversed and both combined and Stroop posters individually and all combined).

TCS is based on 7 items (eCRF items 12.1 through 12.7) from 12.1 Chorea (FACE) through 12.7 12.7 Chorea (LLE).

TFC is based on 5 items for a score between 0 (worst) to 13 (best).

FA is based on 25 item with Yes (1), No (0) answers to get a score between 0 (worst) to 25 (best).

BA is based on 16 items with a score of 0 (best) to 93 (worst)

IS is a single assessment with scores from 10 (worst) to 100 (best)

Cognitive scores are based on 5 items that are added up with a score from 0 to > 300 with higher scores being better. The 5 items include SDMT, SWR.

In addition to the above scores derived from the UHDRS the following additional secondary endpoints will be derived:

CIBIS from 1 (Normal) to 7 (Among the most extremely ill patients). 0 is not assessed and will not be summed.

Body Mass Index (BMI) (Kg/m2)

The Hamilton Depression (HAM-D) Rating Score provides an indication of depression using 17 items rating symptoms from 0 (absent); 1 (mild); 2 (moderate); 3 (severe) to 4 (incapacitating)

- Rate of change (slope) per year from baseline to post baseline Visits V3, V7 and V11 with V11 being most important
- Responder analyses may be generated after review of initial results on changes from baseline described above.

For computation of rate of change (slope) each subject's value will be associated with number of days from Baseline when it was recorded. The rate of change (slope) per day will then be multiplied by 365.25 to be expressed as a rate of change (slope) per year to compare with published literature.

All participants performed CNS MRI (performed in 1.5T) at V-3 visit and at V11 (after the last infusion).

Select MRI Parameters analyzed will include from V-3 (Baseline for MRI) through V11:

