#### 7.4.2. Analysis on Secondary Efficacy Endpoint

Continuous secondary efficacy endpoints will be analyzed as indicated above for the primary efficacy endpoint.

Categorical efficacy data will be analyzed using a Fisher's exact test.

Responder analysis may be performed using thresholds for responders using logistic regression. Covariates for logistic regression will include baseline value of the dependent variable

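### The Baseline TMS main effect in the primary model does not adjust the slope contrast for baseline; prespecify Baseline TMS×Day, with the response and the coding of Day (cheap improvement)

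*SAP*

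**What the plan says.** SAP 4.1.1 defines the endpoint: "The primary efficacy endpoint is rate of change (slope) per year from Baseline to V11 in total motor score (TMS) from the UHDRS". SAP 7.4.1 states: "Analysis will be performed on observed data using MMRM". On the fixed effects it says: "The model will include the following effects: Treatment, Baseline TMS, Treatment \* Day interaction". On covariance: "The unstructured covariance matrix for repeated observations within participants will be used", with six simpler fallback structures that include AR(1) and CS. SAP 7.4.2 carries the model over: "Continuous secondary efficacy endpoints will be analyzed as indicated above for the primary efficacy endpoint".

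Two things are left open. The response is not named: it could be TMS, change in TMS, or an annualised rate. The coding of Day is not stated either. SAP 4.1.2 points to continuous time: "For computation of rate of change (slope) each subject's value will be associated with number of days from Baseline when it was recorded", with the daily slope then multiplied by 365.25. SAP 7.1 points to visits: "All descriptive statistical summaries and statistical inferences will be performed based on nominal visits (visits at which data are collected". SAP 7.4.1 also reports least-squares means at each post-baseline visit.

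SAP 7.4.1 further expects off-schedule visits because of COVID-19 and allows the model to change. SAP 7.2.1 imputes no missing efficacy data. Protocol 6.4 describes the randomisation list and mentions no stratification factor.

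**The concern.** The hypothesis is about slopes, so the quantity tested is a Treatment×Day contrast. A covariate that enters only as a main effect moves a participant's fitted line up or down by the same amount at every visit. A reader who sees Baseline TMS in the model may take the slope comparison to be baseline-adjusted when it is not. The protocol's own model (section 8.7.1.1.1) took the end-of-treatment motor score as response with the baseline measurement as covariate, and there the main effect does act on the comparison. The property was lost in the move to slopes.

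At stake is chance imbalance. Only 7 participants receive placebo, and entry requires a motor score of at least 5 with no upper limit. If participants with higher baseline TMS progress at a different rate and fall unevenly between groups, the slope contrast carries that difference.

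**Working it through.** **Inputs from the documents.** 35 participants, 14:14:7; primary contrast 28 pooled active against 7 placebo; 11 post-baseline visits at 30 to 330 days; two-sided 5% level. The sample size has no statistical basis, so there is no power figure to reproduce.

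**Assumed, not in the documents.** r, the correlation of baseline TMS with slope: 0 to 0.5. For the model fits: baseline SD 12, mean slope 4 points/yr, slope SD 3 given baseline, noise SD 3, and slope rising 0.06 (or 0.10) points/yr per baseline point.

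**Step 1: algebra.** With common days and a fixed covariance, each participant's data reduce to a fitted intercept and slope. The intercept equation has treatment and baseline as regressors; the slope equation has treatment only. These are seemingly unrelated regressions in which the slope regressors are a subset of the intercept regressors. Generalised least squares then returns the unadjusted slope difference.

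**Step 2: fitted models, covariance estimated.** 40 simulated data sets per row. Mean absolute change in the slope contrast (points/yr) from a model with no baseline term:

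| Data, structure, response | Main effect only | Plus Baseline×Day |
|---|---|---|
| Complete, UN, change | 0.000 | 0.43 |
| Complete, UN, TMS | 0.000 | 0.26 |
| Complete, CS, change | 0.000 | 0.34 |
| Complete, CS, TMS | 0.000 | 0.23 |
| Complete, AR(1), change | 0.016 | 0.26 |
| Complete, AR(1), TMS | 0.57 | 0.70 |
| Irregular and missing, CS, change | 0.026 | 0.35 |
| Irregular and missing, CS, TMS | 0.15 | 0.43 |
| Irregular and missing, AR(1), change | 0.10 | 0.35 |
| Irregular and missing, AR(1), TMS | 0.91 | 1.12 |

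The other fallback structures, and UN with missing data, were not checked.

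**Step 3: is a shift an adjustment?** No treatment effect, baseline imbalance fixed at 0.6 SD = 0.6 × 12 = 7.2 points, 150 data sets per scenario. Mean contrast with no baseline term, with the main effect, and with Baseline×Day:

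- Complete data, expected bias 0.06 × 7.2 = 0.43. CS: 0.429, 0.429, −0.003. AR(1) on change: 0.438, 0.436, 0.011.
- Irregular days and dropout, expected bias 0.10 × 7.2 = 0.72. CS on change: 0.906, 0.912, 0.159. AR(1) on change: 1.007, 1.006, 0.200.

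The Monte Carlo standard error of each mean is about 0.15 to 0.24; comparisons within a scenario are tighter because the data sets are shared. Over all scenarios the main effect moved the mean contrast by at most 0.11, in either direction. Baseline×Day moved it by 0.43 to 0.81 from the main-effect model.

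**Step 4: size of chance imbalance.** The SD of the standardised baseline difference is √(1/28 + 1/7) = 0.42. P(imbalance above 0.5 SD, either direction) = 2 × [1 − Φ(0.5/0.4226)] = 0.24. A 0.5 SD (6-point) imbalance biases the contrast by 6 × 0.06 = 0.36 points/yr, or by 0 to 0.60 for coefficients of 0 to 0.10. In general, an imbalance of k standard errors shifts the slope contrast by about r × k of its own standard errors.

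**Step 5: type I error (per-participant slopes, not the MMRM).** Over all randomisations it is about 5% for every r from 0 to 0.5. In the 13% of randomisations with imbalance beyond 1.5 standard errors, the unadjusted test gives about 8% at r = 0.3, 10 to 11% at 0.4 and 12 to 13% at 0.5. With the baseline term acting on slope it gives about 4 to 6%.

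**Step 6: precision.** Variance with the term relative to without is (1 − r²) × (1 + 1/31), where 31 = 35 − 2 − 2. This gives 1.03 (r = 0), 0.99 (0.2), 0.94 (0.3), 0.87 (0.4) and 0.77 (0.5). Break-even is at r² = 1/32, so r = 0.18.

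**The case against.** The strongest reply is that the SAP fixes neither the response nor the coding of Day, so the point rests on one reading. This stands in part. If Day is nominal visit and the response is change, the main effect acts directly on the V11 contrast (mean absolute shift 0.20 points under the assumptions above). If the response is the annualised V11 rate, it also acts directly (0.28 points/yr). Continuous Day is still the more natural reading, given days from Baseline and the factor 365.25.

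A reader might infer that the covariate does nothing at all, whatever the covariance structure. That goes too far. The algebra holds for a fixed covariance, but an MMRM estimates it, and the estimate depends on the mean model. Under AR(1) with TMS as response, the main effect moved the contrast by 0.57 points/yr on average even with complete data, and cut its standard error from 6.1 to 3.1. The SAP also expects irregular and missing data. These shifts come from covariance weighting and missingness, and Step 3 shows little removal of the baseline-related bias.

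A reader might also infer that the primary test is invalid. It is not: over all randomisations the contrast is unbiased and holds its level. The raised error rates are conditional on a minority of allocations and on an assumed r.

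Nor do the documents show that baseline TMS predicts slope. The severity subgroups in SAP 7.4.3 are optional and address differences in treatment effect. SAP 7.2.2 allows an analysis of post- minus pre-treatment slope, with the latter derived from baseline TMS. That is a partial remedy, but also optional.

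Finally, the fitted models showed no clear precision gain (UN on change: 1.66 to 1.64; CS on change: 1.52 to 1.55). That is expected: the assumed coefficient implies r = 0.72/√(3² + 0.72²) = 0.23, near break-even.

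**Conclusion.** The point holds under a stated condition. With continuous Day and TMS or change in TMS as response, the listed Baseline TMS term does not model the dependence of slope on baseline. The exact zero for complete, on-schedule data under UN or CS does not depend on the assumed SDs and slopes; every other simulated magnitude does. The consequence is conditional bias of about r × k standard errors for an imbalance of k standard errors, with r unknown. At r = 0 nothing is lost by leaving the term out; at r = 0.5 its omission costs material precision and conditional error control. This is a cheap improvement, not a flaw that invalidates the primary analysis. SAP 7.4.1 lets the model change, so the term should be prespecified and not chosen after results are seen.

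**What to change.** In SAP 7.4.1, state the response and state that Day is continuous (actual days from Baseline). List the fixed effects as Treatment, Day, Treatment×Day, Baseline TMS centred at its overall mean, and Baseline TMS×Day, or justify omitting the last. Keep the main effect. Naming Day alongside Treatment×Day only reparametrises the arm-specific slopes.

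Make the same change in SAP 7.4.2 for each continuous secondary slope, using that endpoint's own baseline. MRI measures have only V-3 and V11, so a baseline main effect on their change or annualised rate already suffices.

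If nominal visit with change from baseline is intended instead, say so. The main effect then adjusts the V11 contrast. Baseline×Visit is optional, because it adds up to 10 parameters (11 visits minus one) with 35 participants.

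The cost is one parameter per model, one line of code, and about 3 to 4% in variance if baseline is unrelated to slope. No new data are needed.

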The functional evaluation (F) includes an independence checklist scale and an assessment of total functional capacity (TFC - Total Functional Capacity). The functional Checklist is included in a questionnaire of 25 questions that include various tasks of daily living, which are filled out through the information provided by the patient or his companion, in an affirmative or negative way. Each affirmative answer corresponds to one point, and the maximum score of 25 points represents greater functional capacity. A "Total Functional Capacity" (TFC), assesses the participant's ability to perform elementary, basic and instrumental daily life tasks such as maintaining profession and employment, taking care of oneself, managing finances, doing personal hygiene and food. This classification is made by the Investigator and/or person delegated by him, integrating both the information of the patient and his/her family members. The TFC score may vary between scores 0 and 13, and the higher the score, the higher the functionality. Finally, the evaluation is complemented by an independence scale which classifies as a percentage the degree of dependence of the participant, and 100% corresponds to total independence, that is, greater functional capacity (Barreto, 2009; Januário, 2011; Huntington Study Group, 1996).

This scale will be performed at all study visits.

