#### 5. Statistical Hypothesis

This study is a Phase II study to determine efficacy and safety of Cellavita HD. Hypothesis tests for efficacy will be conducted as described below. No hypothesis testing will be performed on any safety data.

All hypothesis tests will be at the two-sided 5% significance level (Two-sided Type I error of 0.05)

H0: There is no difference in rate of change (slope) per year from Baseline through V11 in TMS between the two pooled active treatment groups and the placebo group

Ha: There is a difference in rate of change (slope) per year from Baseline through V11 in TMS between the two pooled active treatment groups and the placebo group

The following statistical tests will be performed:

- 1. Between the two active pooled treatment groups and placebo (primary)
  Participants receiving either 1 million or 2 million cells per kg (Treated) vs. Placebo
- Between each of the two active treatment groups individually and placebo (to determine efficacy of each treatment group compared to placebo)
   Participants receiving 1 million cells per kg (Treated) vs. Placebo
   And Participants receiving 2 million cells per kg (Treated) vs. Placebo
- 3. Between the two active treatment groups to assess similarity between the two treatment groups.

F-SA-06-01, Version 5.0/30 Dec 2021, SOPs Link: SOP-SA-06

Participants receiving 1 million vs. 2 million cells per kg.

The same tests performed for TMS will also be performed for other continuous endpoints.

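### The primary TMS slope model leaves the visits, the coding of Day and the SE/df method unstated; on one well-supported reading its type I error is about 15%, not 5%

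*SAP*

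**What the plan says.** SAP section 4.1.1 defines the endpoint: "The primary efficacy endpoint is rate of change (slope) per year from Baseline to V11 in total motor score (TMS) from the UHDRS". Section 5 sets the level: "All hypothesis tests will be at the two-sided 5% significance level (Two-sided Type I error of 0.05".

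Section 7.4.1 gives the model: "The model will include the following effects: Treatment, Baseline TMS, Treatment" by Day, the last term being the interaction. On covariance it states: "The unstructured covariance matrix for repeated observations within participants will be used". Six simpler structures follow in a fixed order, to be used only if the model fails to converge. The section also allows the model to be changed, or alternatives to be analysed, because of the small sample and the COVID-19 disruption of visits.

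The visits, the coding of Day and the SE/df method are not stated. Other text points in different directions:

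- **Continuous Day:** under SAP 4.1.2 each participant's "value will be associated with number of days from Baseline when it was recorded", and "The rate of change (slope) per day will then be multiplied by 365.25 to be expressed as a rate of change (slope) per year".
- **All 11 post-baseline visits:** protocol 7.2.5 says of the UHDRS, "This scale will be performed at all study visits".
- **Day as a visit factor:** SAP 7.1 says "All descriptive statistical summaries and statistical inferences will be performed based on nominal visits (visits at which data are collected". Section 7.4.1 presents least-squares means and confidence intervals at each post-baseline visit.
- **Three visits:** SAP 4.1.2 (secondary endpoints) and the descriptive summaries in 7.4.1 name slopes to V3, V7 and V11.

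Section 7.4.2 applies the same analysis to the continuous secondary endpoints.

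**The concern.** An unstructured matrix over 11 visits has 11 × 12 / 2 = 66 parameters, estimated here from 35 people. When the mean model is a straight line, the estimated matrix also sets how the visits are weighted to form the slope. The usual model-based SE treats those weights as known and so understates the uncertainty. With only three visits there are 3 × 4 / 2 = 6 parameters and the effect is small. With Day as a visit factor the mean model is saturated and, on complete data, the effect disappears.

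Two programmers could both follow this SAP faithfully and run primary tests with very different false-positive rates. The ordered list of simpler structures is aimed at a model that fails to converge. The trouble here is a model that converges and reports too small an SE.

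**Working it through.** **Inputs from the documents.** Two-sided 5% (SAP 5). Allocation 14:14:7, so 28 pooled active against 7 placebo (protocol 4.3, SAP 3). Visits 30 days apart to day 330 (SAP 3). The sample size has no statistical derivation, so the only figure to reproduce is the 5% level.

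**Closed form (complete data, two arms, no SDs needed).** Let m = 35 − 2 = 33, and k = visits minus mean parameters per arm.

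- Estimated/true variance of the slope = (m − k)/m × (m − k − 1)/(m − 1).
- SE ratio = square root of that.
- Type I error = two-sided tail of t on m − k df beyond 2.037 × SE ratio, where 2.037 is the 5% critical value on 32 df.

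| Reading | k | Variance ratio | SE ratio | Type I error |
|---|---|---|---|---|
| 11 visits, Day as factor | 0 | 1.000 | 1.000 | 5.0% |
| V3/V7/V11, linear Day | 1 | 32/33 × 31/32 = 0.939 | 0.969 | 5.7% |
| 11 visits, linear Day | 9 | 24/33 × 23/32 = 0.523 | 0.723 | 15.4% |

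The SE shortfall in the last row is 1 − 0.723, about 28%. The plan's 5% is reproduced only in the first row. A per-participant slope used as the response by visit also has k = 0, hence 5.0%; that reading was not simulated.

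**Simulation under the null.** 28 v 7, complete monthly data, baseline covariate. Assumed, because the documents give no SDs: intercept SD 12, visit-error SD 4, true slope SD 0/2/4/6 points per year. There were 4,000 runs per cell for uncorrected unstructured fits (t on 32 df) and 2,000 for Kenward-Roger (KR) rows; Monte Carlo SE is 0.3-0.6 points.

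| Analysis | Type I error (%) at slope SD 0/2/4/6 |
|---|---|
| Unstructured, 11 visits, linear | 14.9 / 14.9 / 15.8 / 14.6 |
| Unstructured, 11 visits, factor, V11 contrast | 5.9 / 5.0 / 5.5 / 5.0 |
| Unstructured, V3/V7/V11, linear | 6.3 / 5.5 / 5.9 / 5.4 |
| Unstructured, 11 visits, linear, KR | 8.2 / 7.6 / 8.4 / 7.2 |
| Random intercept and slope, KR, baseline as covariate | 4.4 / 4.6 / 4.7 / 4.4 |
| Random intercept and slope, KR, baseline as day-0 response | 4.0 / 4.7 / 5.5 / 4.5 |

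**Sensitivity.**

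- A separate simulation (assumed baseline SD 10, slope SD 4, residual SD 4) gave 15.3% for 11 visits with linear Day and pooled arms, and 16.3% with three arms. A z reference gave 16.7% and 17.9%.
- With a z reference the other simulated readings rise to about 6-7%.
- AR(1) data gave 15.6%.
- With 5 of 35 dropping out at random the figure was 19.6%.
- Satterthwaite df without an SE adjustment left about 16%. Kenward-Roger gave 7.8% with 11 visits and 4.4% with V3/V7/V11.
- With irregular visit timing (assumed mean of 10 extra days per gap), unstructured with linear Day gave 15.0-17.3% (1,000 runs). The random-slope model gave 3.4-6.0% (500 runs, SE about 1 point).

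**The case against.** The 15% needs three unstated choices together: 11 visits, linear Day and no correction. The support for that combination is indirect. Protocol 7.2.5 says when the scale is collected, not what enters the model. The text on days and 365.25 sits among the secondary endpoints, next to slopes at V3, V7 and V11. Nominal-visit inference and by-visit least-squares means are what an MMRM with visit as a factor normally produces. All of this stands, and it is why the 15% is conditional.

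A reader might infer that the sponsor's primary test will have a 15% error rate. The documents do not support that, because other open readings hold about 5-6%. A reader might also infer that every continuous secondary endpoint is affected. SAP 4.1.2 places MRI at V-3 and V11 only; with one post-baseline value there is no repeated-measures matrix, so the mechanism cannot arise there.

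The list of simpler structures might still be triggered in practice. Unstructured fits converged in the simulations, on complete data and in one random-dropout run, but SAS was not run on the trial's actual missing data.

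Kenward-Roger may be the programmer's habit, but the SAP does not name it, and it leaves 7-8% on the 11-visit linear reading.

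Finally, the main evidence for the random-slope model comes from data generated by such a model, without dropout. It is a well-matched choice for a slope endpoint, but not the only valid one.

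**Conclusion.** The concern holds as a gap in specification with a conditional consequence. Section 7.4.1 puts unstructured covariance first and keeps it whenever it converges. On a reading supported by SAP 4.1.1, SAP 4.1.2 and protocol 7.2.5, that rule gives an SE about 28% too small and a type I error of about 15% against a stated 5%. On complete data the figure hardly depends on the assumed SDs; a z reference or dropout raises it. On the other readings the level is about 5-6% with a t reference.

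The actual level of the primary test therefore depends on choices left to programming, and the open permission to change the model widens that choice. The issue extends to continuous secondary endpoints measured repeatedly, not to MRI. It should be fixed, and the case for fixing it does not require showing that the 15% version was intended.

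**What to change.** 1. State which visits enter the primary model, and that Day is actual study day, continuous. State that the nominal-visit rule in SAP 7.1 governs by-visit tables only.
2. Do not combine unstructured covariance with linear Day over 11 visits. Use a random intercept and slope per participant, fitted by REML with Kenward-Roger SE and df. Report the arm-by-day difference × 365.25 with its 95% CI. A visit-factor model with a V11 contrast, or V3/V7/V11 with Kenward-Roger, would also hold the level if the sponsor prefers it and fixes it in advance.
3. State whether baseline TMS is a covariate or the day-0 response, not both.
4. Limit the permission to change the model to named sensitivity analyses.

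Unweighted per-participant slopes compared by t-test should not be added as a fallback. With assumed early dropout (last visit uniform on V1-V9), type I error was about 10-12% when 2 of 7 placebo and 3 of 28 active dropped out, and about 16-20% when only 2 placebo did.

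The cost is SAP wording and a few lines of code; no new data are needed. Reported precision may look less favourable than under the uncorrected model, although the true SD of the slope difference at slope SD 4 is smaller: 2.61 (baseline covariate) or 2.44 (day-0 response) against 3.07. If true slopes hardly vary, the slope variance is often estimated at zero (about 60% of data sets at slope SD 0) and the test is slightly conservative, at 4.0-4.4%.
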